6.2.4 Subgroup analysis

The time to event analysis for the efficacy variables will be repeated by the following subgroups:

- Age group 1 (<60 years, 60-75, >75years)
- Age group 2 (<50yrs/>=50-<60yrs/>=60-<65yrs/>=65-<70yrs/>=70-<80yrs/>=80yrs)
- Sex (male, female)
- Patients with AF (Yes/No)
- Patients with diabetes mellitus (Yes/No)
- Patients with prior CV events (Stroke, TIA, MI, DVT, PE) (Yes/No)
- Patients with prior MACE (Yes/No)
- Patients with ASA / non-ASA
- History of (symptomatic) COVID-19 (Yes/No)
- Symptomatic COVID-19 during the study (Yes/No)

Forest plots showing incidences and hazard ratios will be provided for the comparison of high dose osocimab and placebo and for low dose osocimab versus placebo.

6.3 Pharmacokinetics/pharmacodynamics

There might be some inaccuracies in the actual sampling times compared to planned sampling times due to the fact, that the study procedures orientate on the dialysis schedule rather than specifying exact days for the study procedures. These deviations can be relevant for the interpretation of pharmacokinetic and pharmacodynamic data. Accepted time windows were prespecified in the guidance document for PD validity for study #20115 and will be referenced in the final blind review report. Accepted time windows for the assessment of pharmacokinetic concentrations will be handled analogously.

All valid results will be included in the listings and graphical displays of individual data, which are displayed using actual times. Measurements taken outside the predefined time windows will be flagged by the pharmacokinetic and pharmacodynamic experts to be excluded from the calculation of summary statistics (with respect to planned times) in order to avoid biased results.

For the primary completion analyses all duplicates at the same visit will be excluded for the statistical analyses in section 14 by programming algorithm, and they will be listed only in section 16.2.

For the final analyses all PK data and PD data (aPTT, FXIa activity, FXI activity) flagged as invalid will not be used for the analyses. Duplicates in other PD data at the same visit will be excluded for the statistical analyses in section 14 by programming algorithm, and they will be listed only in section 16.2.

PK variables

Osocimab concentrations will be summarized by visit, separated according to actual dose cohort. Descriptive statistics of plasma concentrations [geometric mean and percent coefficient of variation (%CV), arithmetic mean and %CV, median and range] will be presented by treatment group and time in tabular form. Means at any time will only be calculated if at least 2/3 of the individual data were measured and were above the lower limit of quantification (LLOQ). For the calculation of the mean value, a data point below LLOQ will be substituted by one half of this limit. In tables showing mean values, where values below LLOQ are included in the calculation of mean values, these means will be marked. Box plots for osocimab trough levels will be provided by treatment.

For all treatments where at least one subject with at least one confirmed ADA formation is included, the individual concentrations of osocimab in plasma will be displayed including supplemental information about the ADA titer. Individual subjects with confirmed ADA formation will be indicated by different colors and symbols. Filled symbols will indicate neutralizing characteristics.

Pharmacokinetic and exposure-response analysis using population approaches (popPK and popPK/PD, e.g., by non-linear mixed effect modeling) will be reported under separate cover, if applicable.

Bioanalysis and population PK (popPK) evaluation might be started prior to database lock: if this is applicable, appropriate measures will be taken to maintain blinding of the study team.

PD variables

All PD analyses will be conducted in the pharmacodynamic analysis set.

The activated partial thromboplastin time (aPTT) and FXIa activity at trough levels after 6 months will be analyzed as ratio to baseline by providing the mean and median, together with the standard deviation and quantiles, respectively.

Results of the additional pharmacodynamics parameters will be displayed utilizing appropriate summary statistics and figures. The parameters will be described by the following summary statistics: arithmetic mean, standard deviation, median, minimum, and maximum. These summary statistics will be presented by actual dose group for the original data as well as for the absolute and relative changes from baseline as ratio to baseline. In addition, for each subject the maximum and minimum relative change from baseline will be determined and presented by appropriate summary statistics and figure.

In addition, a scatter plot of the following pairs of parameters by time point is provided to evaluate the correlation, the first parameter on the y-axis and the second parameter on the x-axis:

Parameter on y-axis	Parameter on x-axis
aPTT	FXIa activity (AXIA assay)

aPTT	FXI activity (clotting assay)
aPTT	FXI concentration
aPTT	Plasma concentration of osocimab
FXIa activity (AXIA assay)	FXI activity (clotting assay)
FXIa activity (AXIA assay)	FXI concentration
FXIa activity (AXIA assay)	Plasma concentration of osocimab
FXI activity (clotting assay)	FXI concentration
FXI activity (clotting assay)	Plasma concentration of osocimab
FXI concentration	Plasma concentration of osocimab
D-dimer	aPTT
D-dimer	FXIa activity (AXIA assay)
D-dimer	FXI activity (clotting assay)
D-dimer	Plasma concentration of osocimab
TAT	aPTT
TAT	FXIa activity (AXIA assay)
TAT	FXI activity (clotting assay)
TAT	FXI concentration
TAT	Plasma concentration of osocimab
F1.2	aPTT
F1.2	FXIa activity (AXIA assay)
F1.2	FXI activity (clotting assay)
F1.2	FXI concentration
F1.2	Plasma concentration of osocimab

These plots will be repeated using a semi-logarithmic scale.

It is important to present the PD tables and figures in the following order:

- aPTT,
- FXIa activity (AXIA),
- FXI activity (clotting assay),
- FXI concentration,
- D-dimer,
- TAT,
- F1.2

The scatterplots will be sorted by the parameter on the y-axis.

The exploratory PD marker results may be reported separately.

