### 8.2.2.1 Assessment of AV Access Bleeding

Severity of bleeding at the dialysis access will be assessed approx. 15 minutes after removal of the dialysis needle(s) from the AV access according to the following categories (exploratory bleeding score):

- “0” no access bleeding
- “1” slow oozing
- “2” overt bleeding

In case the AV access exhibits overt bleeding 15 minutes after removal of the dialysis needle(s) (AV access bleeding score of 2), the investigator may consider the reduction of heparin (i.e. UFH, LMWH) for the subsequent dialysis sessions during the treatment and follow-up period. For such decision, the investigator should take all available participant information into account (e.g., laboratory values, concomitant medication, details of hemodialysis session, adverse events etc.).

In case catheter is used, the AV access bleeding is not applicable.

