## 8.6 Pharmacodynamics

For the investigation of the pharmacodynamic response to osocimab and its relationship with treatment effects, pharmacodynamic parameters detailed below will be determined at different time points using a sparse sampling approach in all participating subjects. Details about the collection, processing, storage and shipment of samples will be provided separately (e.g., in the laboratory manual). Samples from participants not treated with osocimab will also be analyzed.

Blood samples will be collected at the time points indicated in the SoA (Section 1.3). Blood samples obtained at additional time points based on the investigator's discretion will not qualify as a protocol deviation and will be used for the PD analysis as well. Deviations from the specified time points will be documented and taken into account for the PD analysis. Date and time of the PD sample collection and date and time of most recent study drug administration must be documented accurately in the eCRF.

For PD evaluation of osocimab the last sample taken prior to first drug administration will be defined as reference time point (i.e., will be assigned to a relative time of 00d00h00m).

The actual date and time of blood sampling will be collected in the eCRF. All PD parameters will be measured using validated methods. Quality control and calibration samples will be analyzed concurrently with study samples. For selected parameters, results of QC samples will be reported together with analyte concentrations in the Clinical Study Report (CSR) for this study. Concentrations of the analyte are calculated according to the method description. Detailed method descriptions of all PD methods will be filed with the CSR for this study.

The following parameters will be used to assess the PD effects after administration of the investigational drug:

Main pharmacodynamic parameters:

- aPTT will be measured via the kaolin-trigger method (clotting assay). Furthermore, the aPTT assay will be conducted after in vitro-neutralization of heparin in order to separate potential heparin effects from the PD effect of osocimab.
- Factor XI activity will be assessed with an aPTT-based coagulation test using FXI deficient plasma. Furthermore, the assay will be conducted after in vitro-neutralization of heparin in order to separate potential heparin effects from the PD effect of osocimab.

Other pharmacodynamic parameters:

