### 9.4.3 Secondary Endpoints

The activated partial thromboplastin time (aPTT) and FXIa activity at trough levels after 6 months will be analyzed as ratio to baseline by providing the mean and median, together with the standard deviation and quantiles, respectively.

The exploratory composite efficacy endpoint will be analyzed using a time to event analysis similarly to the primary safety endpoints. Thus, the descriptive analysis focuses on estimating the efficacy under an osocimab concentration which is expected to be maintained during a chronic treatment.

Only events that started after the first dose of study treatment and during the main treatment period are considered for the primary analysis. Events that occurred during the pre-treatment period will be displayed in an exploratory manner.

The endpoint of thrombosis of the arterio-venous grafts or fistulas will be handled similar.

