TE	Thromboembolic
UFH	Unfractionated heparin
VTE	Venous thromboembolism
WBC	White blood cell

1. Introduction

Osocimab is a novel long-acting anticoagulant targeting the activated form of FXI with the potential to exhibit lower risk of bleeding events than currently available anticoagulants.

It is well known that ESRD patients on dialysis are at high risk for cardiovascular diseases. By targeting FXI, osocimab has the potential to provide an efficacious treatment for the prevention of thromboembolic events like MI, stroke, and cardiovascular death with a favorable risk profile for unwanted bleeding. This Phase 2b trial will assess the safety and characterize the PK/PD profile of two different dose cohorts of osocimab given subcutaneously once a month to subjects with ESRD.

Further information can be found in the clinical study protocol.

2. Study Objectives

Objectives and endpoints are listed in the table below:

Objectives	Endpoints
Primary	

 To clinically assess the safety and tolerability of different doses of osocimab administered subcutaneously once a month during main treatment period as compared to placebo 	
 Composite of major and clinically relevant non-major bleeding events (in alignment with the ISTH guidelines) as assessed by blinded central independent adjudication committee (CIAC) Composite of moderate and severe AEs and SAEs
Secondary	

 To assess the change of key PD parameter from baseline 	
 aPTT, FXIa activity at trough levels after 6 months
Tertiary/Exploratory	

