4.6 Blind Review

There will be two data assessment lists. The first one will occur after primary completion and the second one will occur after end of study. The results of both data lists will be documented in separate lists of important deviations, validity findings and assignment to analysis set(s). Any changes to the statistical analysis prompted by the results of the review of study data will be documented in an amendment and, if applicable, in a supplement to this SAP.

The results of the final data assessment will be documented in the final list of important deviations, validity findings and assignment to analysis sets. Pharmacodynamic values to be excluded from statistical analysis will be documented in the list of pharmacodynamic values to be flagged as invalid.

5. Analysis Sets

Final decisions regarding the assignment of subjects to analysis sets will be made during the review of study data and documented in the final list of important deviations, validity findings and assignment to analysis set(s) (see section 4.6).

The following populations are defined:

Population	Description
Enrolled	All subjects who sign the ICF
Full Analysis Set	All subjects randomly assigned to study intervention.
Safety Analysis Set	All subjects randomly assigned to study intervention and who took at least 1 dose of study intervention. Subjects will be analyzed according to the intervention they actually received.
Pharmacokinetic analysis set	All osocimab-treated subjects with at least 1 PK sample in accordance with the PK sampling schedule (Section 1.3 and Section 8.5 of the study protocol) and without deviation from the protocol that would interfere with the evaluation of the PK data will be included in the PK analysis.
Pharmacodynamic analysis set	All subjects with at least 1 PD sample in accordance with the PD sampling schedule and without deviation from the protocol that would interfere with the evaluation of the PD data will be included in the PD analysis.
Listing only set	All subjects who signed ICF but are not randomized.

In accordance with the “population” attribute of the primary estimand, the primary analysis set is the safety analysis set.

Supplementary analyses of the efficacy variables will be performed on the full analysis set.

6. Statistical Methodology

In general, the evaluations will be conducted on each osocimab group and on the placebo group.

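### The secondary PD endpoint has no planned osocimab-versus-placebo contrast, and the SAP does not say which aPTT assay it uses

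*SAP*

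**What the plan says.** The secondary endpoint is aPTT and FXIa activity at trough after 6 months. SAP 6.3 (PD variables) says that both "will be analyzed as ratio to baseline by providing the mean and median, together with the standard deviation and quantiles, respectively". Protocol 9.4.3 agrees: the two markers "at trough levels after 6 months will be analyzed as ratio to baseline by providing the mean and median". For the additional PD parameters, SAP 6.3 says they are "described by the following summary statistics: arithmetic mean, standard deviation, median, minimum, and maximum". For PK concentrations it names "geometric mean and percent coefficient of variation (%CV), arithmetic mean and %CV, median and range". No geometric mean, model, group difference or interval is named for any PD variable.

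The secondary objective (SAP Section 2) is "To assess the change of key PD parameter from baseline". The opening of SAP Section 6 adds that in general "the evaluations will be conducted on each osocimab group and on the placebo group". Protocol 8.6 has PD samples from untreated participants analysed, whereas Protocol 8.5 makes PK analysis of such samples optional.

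On the assay, Protocol 8.6 lists kaolin-triggered aPTT as a main PD parameter and adds that "the aPTT assay will be conducted after in vitro-neutralization of heparin in order to separate potential heparin effects from the PD effect of osocimab". It repeats this for FXI activity by clotting assay. No neutralised version of the FXIa activity (AXIA) assay is described. The SAP does not mention a neutralised result.

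Heparin for dialysis is allowed throughout (Protocol 4.1). After overt access bleeding, "the investigator may consider the reduction of heparin" for later sessions (Protocol 8.2.2.1).

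**The concern.** There are two gaps. First, the trial has a concurrent placebo group with PD data at baseline and month 6, but the plan does not estimate the osocimab effect relative to that group. A within-group ratio to baseline combines the drug effect with anything else that shifts aPTT over six months, and it comes with no statement of precision.

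Second, the variable is not uniquely defined. The protocol plans two versions of the assay because heparin can prolong aPTT, and the SAP does not say which version enters the ratio. Heparin use can change after randomisation and could change differently between groups. The choice of version can then alter the estimate, and it would be made after the data exist.

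At stake is how clearly the only secondary endpoint can be read as a placebo-controlled PD effect.

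**Working it through.** **1. Between-group statistics planned, by endpoint**

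| Endpoint | Rank | Osocimab versus placebo | Place |
|---|---|---|---|
| Bleeding composite; AE composite | Primary, descriptive | Hazard ratios with 90% and 95% CIs, log-rank tests, difference in cumulative incidence with 90% CI | SAP 6.4.1 |
| Clotting score (SQCS) | Exploratory | Mean difference with 90% and 95% CIs (ANOVA), Wilcoxon test | SAP 6.2.3 |
| AV access bleeding score | Exploratory | Same | SAP 6.4.3 |
| aPTT, FXIa activity at month 6 | Secondary | None | SAP 6.3 |

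The descriptive status of the trial does not explain the last row, because every row is descriptive.

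**2. Which aPTT?** Protocol 8.6 gives two versions. Protocol Table 10–1 also lists aPTT in the central coagulation panel. As far as the Schedule of Activities can be read, that panel and the main PD samples both fall at visit 5 (the PD baseline under SAP 4.5) and at the EOMT visit. Up to three aPTT values could therefore exist at each end of the ratio. In SAP 6.3 the endpoint sentence, the scatter-plot list and the table order all say only aPTT.

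**3. Numbers available.** The plan's own figure is 555 completers (Protocol 9.2): 600 × (1 − 0.15 × 0.5) = 555.0, or 600 × exp(−0.075) = 556.6. It reproduces. Per group, 555 / 3 = 185 is a ceiling for month-6 PD data, because sites in China give no PD samples (Protocol 10.6, number not stated). I take 120 as an assumed lower case.

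**4. Precision of a placebo contrast.** For a ratio of geometric means, the 90% CI multiplies and divides the estimate by exp(1.645 × s × √(2/n)), where s is the SD of the log ratio. The documents give no s, so the range is assumed.

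| s | n = 185 | n = 120 |
|---|---|---|
| 0.1 | 1.017 | 1.021 |
| 0.2 | 1.035 | 1.043 |
| 0.3 | 1.053 | 1.066 |
| 0.5 | 1.089 | 1.112 |

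**5. Adjusting for baseline.** If log variances are equal at baseline and month 6 with correlation ρ, the variance under ANCOVA divided by that of the simple log ratio is (1 + ρ)/2. For ρ = 0.3 to 0.7 (assumed) this is 0.65 to 0.85, a reduction of 35% to 15%. Equal variances are doubtful when two of three groups receive a drug that shifts the measure, so this is indicative only.

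**6. Heparin, illustration only.** Assume heparin multiplies aPTT by 1.10 when present and the true drug ratio is 1.50.
- Present at baseline only: 1.50 / 1.10 = 1.36.
- Present at month 6 only: 1.50 × 1.10 = 1.65.
- Present at both: 1.50 × 1.10 / 1.10 = 1.50.

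If both groups lose the heparin effect equally, placebo reads 1 / 1.10 = 0.909, and the contrast 1.364 / 0.909 returns 1.50. If only the osocimab group loses it, placebo reads 1.00 and the contrast stays at 1.36. A placebo contrast therefore removes shared drift, and only the neutralised assay addresses differential drift.

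**7. Choice of mean.** For log-normal ratios, arithmetic over geometric mean is exp(s²/2): 1.005 (s = 0.1), 1.020 (0.2), 1.046 (0.3), 1.133 (0.5).

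**The case against.** The strongest reply is that the analysis matches its objective. That objective is change from baseline and, unlike the primary one, does not mention placebo. The trial has no formal hypothesis (Protocol 9.1), and placebo is tabulated beside the osocimab groups. The SAP also plans scatter plots of aPTT and FXIa activity against concentration, and foresees population PK/PD modelling under separate cover. All of this is correct. It shows that a contrast would be an addition and not a repair. It does not explain why the exploratory scores get intervals and the secondary endpoint does not.

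On heparin, PD samples are drawn before dialysis, patients with aPTT above the upper limit of normal are excluded (Protocol 5.2), and heparin dose is summarised as change from baseline (SAP 6.4.8). Reduction is optional, and more frequent reduction on active drug is conjecture. These points limit the effect without excluding it: sampling from the dialysis line or a tunneled catheter is permitted (Protocol 8.2.6), and the protocol judged heparin important enough to plan a second assay.

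Three stronger readings are tempting, and the documents do not support them.
- A reader might infer that dose selection for Phase 3 would rest on a skew-inflated arithmetic mean. Medians and quantiles are planned in the same sentence and are robust to skew. The inflation is under 5% if s is 0.3 or less (assumed). That the mean is arithmetic is itself an inference from its pairing with an SD.
- A reader might infer that there is no comparison with placebo at all. Only a formal contrast and interval are missing.
- A reader might infer that the SAP discards the neutralised assay. It is silent on the version, which is ambiguity and not exclusion.

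**Conclusion.** The concern holds as a low-severity, low-cost improvement. Two things are missing from SAP 6.3: an osocimab-versus-placebo contrast with an interval for aPTT and FXIa activity at month 6, and a statement of which aPTT assay is the endpoint. Nothing stated in the plan is numerically wrong.

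With 120 to 185 per group and s between 0.1 and 0.5, the contrast would have a 90% CI factor of about 1.02 to 1.11. Those values of s, and the 120, are assumptions. The heparin effect cannot be sized from the documents: 1.36 and 1.65 against a true 1.50 show only what an assumed 10% change at one time point would do. The assay point applies to aPTT and not to FXIa activity.

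**What to change.** In SAP 6.3, with Protocol 9.4.3 aligned:

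1. For aPTT and FXIa activity, add an ANCOVA of the log month-6 trough value with treatment group and log baseline (visit 5, pre-dose). Report geometric mean ratios of each osocimab group versus pooled placebo with 90% CIs. Keep the planned medians and quantiles.
2. Name the heparin-neutralised aPTT as the secondary variable and the standard kaolin aPTT as supportive. Say whether the coagulation-panel aPTT plays any part. Make no such change for FXIa activity, as no neutralised assay is described.

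The cost is SAP wording and one standard model. No new sample or visit is needed, and the assays are already planned, although Protocol 8.6 lets the sponsor omit some; the neutralised aPTT would have to be kept. SAP 6.5 indicates that the primary analysis was complete before the current SAP version, so at this stage the added analysis should be labelled as specified after unblinding.

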6.4 Safety

6.4.1 Primary safety variables

The composite of major bleeding (MB) and clinically relevant non-major bleeding (CRNMB) events, as assessed by CIAC, and the composite of moderate and severe AEs and SAEs will

be the primary safety endpoints in this study. Only events that started after the first dose of study treatment and during the main treatment period are considered for the primary analysis.

For the primary safety analysis descriptive time to first primary safety event (both treatment emergent AEs and composite of treatment emergent major and CRNMB events [in alignment with ISTH guidelines]) analyses will be performed.

According to the description of the primary estimand, the following events will be considered as competing events for the respective safety endpoint:

- death
- premature end of exposure to assigned treatment (last administration of assigned treatment plus 30 days).

For the primary analysis, the time to event for a subject will be censored at the date of the EOMT visit or after no further data collection happened for a subject (e.g. lost to follow-up).

According to the study protocol (section 7.1.1) one maintenance dose can be missed. If a subject misses a maintenance dose, has a so called administration gap, that lasts longer than 30 days, the subject is not considered at risk for treatment-emergent events during this time until the next dose. When the subject then takes a maintenance dose again, he/she is at risk again. Accordingly there will be additional analyses, where the time not under exposure between two doses will be ignored and events during that time will not be counted. The time under risk will be calculated by removing time between the interrupted dose + 30 days and the next dose and the time more than 30 days after permanent discontinuation to study drug and if occurred the 1st event per patient will be counted. For the primary analysis in this data scope, the time to event for a subject will be censored at the date of the EOMT visit or after no further data collection happened for a subject (e.g. lost to follow-up).

The cumulative incidence function for the event-of-interest as well as the associated competing event(s) together with the corresponding confidence interval will be estimated for each treatment arm using Aalen-Johansen estimators.

The competing event for the primary safety endpoint is death and premature discontinuation of exposure to assigned treatment.

The cumulative incidence, i.e. the probability of having a specific event E at or before a timepoint t, $P(T \leq t, E = 1)$, will be estimated for time-to-event endpoints by Aalen-Johansen estimators with the competing event.

The difference of the Aalen-Johansen estimators between high dose osocimab and placebo and low dose osocimab and placebo will be presented with a 90% confidence interval.

As the Aalen-Johansen estimator is approximately normal distributed (Aalen, Borgan and Gjessing 2008), the difference of Aalen-Johansen estimators is approximately normal distributed. Thus, the two-sided 90% confidence interval is obtained via:

$$\left[\widehat{AJ}^{TRT}(day) - \widehat{AJ}^{CON}(day) \pm z_{0.95} \sqrt{\sigma^2(\widehat{AJ}^{TRT}(day)) + \sigma^2(\widehat{AJ}^{CON}(day))} \right],$$

with $\widehat{AJ}^{TRT}(day)/\widehat{AJ}^{CON}(day)$ the Aalen-Johansen estimator for treatment TRT/ control CON at study day, $z_{0.95}$ the 90% quantile of the standard normal distribution and $\sigma^2(\widehat{AJ}^{TRT}(day))$ and $\sigma^2(\widehat{AJ}^{CON}(day))$ the estimated variance of the Aalen-Johansen

estimator for osocimab (treatment, TRT) and placebo (control, CON) at study day, estimated with the Aalen method.

Rates

Cause-specific incidence rates will be calculated for each treatment arm with an 90% confidence interval.

The exposure-adjusted incidence rate will be expressed a “subjects with an event – per 100 participant years”. For that the following formula is used:

$$IR_{adj} = \frac{\#Participants\ with\ an\ event}{\sum\ time\ under\ treatment\ (in\ days)/(100 * 365.25)}$$

The 90% confidence interval for the exposure-adjusted IR will be computed as

$$\left[\frac{IR_{adj} * \chi^2(0.05; 2e)}{2e}, \frac{IR_{adj} * \chi^2(0.95; 2e)}{2e} \right],$$

with $\chi^2(q; 2e)$ the q quantile of a chi square distribution with 2e degrees of freedoms and e the number of participants with an event. (Nelson 1982)

With respect to the cause-specific hazards for the respective safety variable, each of the osocimab groups will be compared to the placebo group using two-sided log-rank tests at a type I error rate of $\alpha=10\%$. Due to the explorative nature of these analyses, no multiplicity adjustment will be done.

Cause-specific hazard ratios, cause-specific relative hazard reduction (csRHR; $csRHR = 100 \times [1 - \text{cause-specific hazard ratio}]\%$), and corresponding 2-sided 90% and 95% confidence intervals, comparing the hazards for the event-of-interest in each of the osocimab groups with the placebo group will be estimated based on two separate cause-specific Cox proportional hazards models. Censoring will be assumed independent of the randomized group assignment.

To complete the analysis, cause-specific HRs will be estimated for (each of) the competing events.

For the analysis of the primary endpoint in this study, the cause-specific hazard function $h_k(t)$ is the chance that an individual experiences an event of the primary safety outcome in the next instant in time, given that the individual has not had such an event or a competing event up to time t. For example, for the comparison of the osocimab high dose group with the placebo group, the corresponding cause-specific Cox proportional hazards model can be described by the following equation:

$$H_k(t, x_i) = h_{0,k}(t) \exp(\beta_k x_i),$$

where

$h_k(\cdot)$ cause-specific hazard function for primary safety outcome, as a function of time and subject's covariates

$h_{0,k}(\cdot)$ unspecified underlying baseline hazard function for primary safety outcome; hazard of an individual with $x_i = 0$

t time (in days) relative to the date of first administration

x_i	treatment group of subject i (0 corresponds to “placebo group” and 1 corresponds to “osocimab high dose group”)
β_k	unknown parameter (to be estimated); cause-specific hazard ratio = $\exp(\beta_k)$
k	type of event

Probability

As a supportive analysis, the cumulative incidence functions for the respective event-of-interest will be compared using the Fine and Grays subdistribution hazards model as well as using the Gray’s test.

